Describe in detail the methods and procedures that will be used to accomplish the objectives and specific aims of the project. Discuss the alternative methods that are available and justify the use of the method proposed in the study. Justify the scientific validity of the methodological approach (biomedical, social, or environmental) as an investigation tool to achieve the specific aims. Discuss the limitations and difficulties of the proposed procedures and sufficiently justify the use of them. Discuss the ethical issues related to biomedical and social research for employing special procedures, such as invasive procedures in sick children, use of isotopes or any other hazardous materials, or social questionnaires relating to individual privacy. Point out safety procedures to be observed for protection of individuals during any situations or materials that may be injurious to human health. The methodology section should be sufficiently descriptive to allow the reviewers to make valid and unambiguous assessment of the project. (DO NOT EXCEED TEN PAGES. USE CONTINUATION SHEETS).

ETEC and *V. cholerae* are the two most common bacterial pathogens causing acute watery diarrhea in children in Bangladesh. The aim is to design and optimize vaccines which will protect against these two infections in young children and infants. To do so we plan to carry out a series of studies, some in parallel and some in sequence, one after the other with the ultimate goal to over the next 3-5 years have a vaccine that will be ready for protective efficacy and effectiveness studies in young children in developing countries like Bangladesh. To achieve this, we will in the first six months initiate studies to determine the optimal formulating liquid for the oral vaccine in young children to determine the suitable liquid composition for the cholera and ETEC vaccines. For this part we will first carry out studies on the cholera vaccine and then on the ETEC vaccine. Having done this we will determine the effect of breast milk (+/-) and zinc (+/-) on the vaccination. These two components will be run in parallel. At first the studies on the cholera vaccine will be carried out and this will be followed by the study on the ETEC vaccine. We hope that with these results we will finally proceed with a modified cholera and ETEC vaccine formulation

Principal Investigator: Last, first, middle [name]

for efficacy studies.

The different components of the vaccine studies are planned and will initiate with the cholera vaccine followed by the ETEC vaccine as follows:

Sample size: The sample size has been calculated in the different interventions, using a one sided hypothesis and confidence of approximately 95%, a minimum detectable difference in mean (MDD) of 50% improvement over baseline, and with 15% for dropout adjustment.

As the whole cell cholera vaccine with standard buffer in subjects aged 2-5 years of age 36% respond with vibriocidal antibodies (Albert et al. 2003, Qadri et al.2004) the sample size of each group in the two buffer components and in the formulation in water will be 102. As our earlier work on ETEC vaccine in Bangladesh we have found on average 55% percent of children in the 6 months to 2 years of age respond with CF specific antibodies (Qadri et al. in manuscript), the sample size of the each group of the breast feeding component will be 57; Using the results obtained on zinc supplementation on the whole cell cholera vaccine in subjects aged 2-5 years of age (Albert et al. 2003, Qadri et al.2004), 36% respond with vibriocidal antibodies before and a 66% responder frequency is seen after the intervention, the sample size of each group on the zinc supplementation component will be 75.

1. The optimum buffer for formulation of the vaccines in children

We would like to evaluate the suitability of the buffer which will be used to formulate the cholera or ETEC vaccine for use in young children. In addition we will also determine if the vaccines can be used without any buffer that is in water in these children. At present we use about 400 mg of the bicarbonate buffer for formulation of the ETEC vaccine for the young children. We plan to evaluate if this amount can be omitted with retained immunogenicity of the vaccines.

We would also like to compare the immunogenicity of the ETEC and/or cholera vaccine after formulation in two different buffers in children. We will formulate the cholera and/or ETEC vaccine in CeraVacx which contains rice syrup solids, sodium bicarbonate and citric acid (Sack DA et al. 1997). Finally we will study the response in a group of children who will receive the vaccine, which has not been formulated in any buffer. The results of these studies will be used to formulate the cholera and ETEC vaccine in the most appropriate dissolving liquid.

Based on this we plan to study three groups of children who will be given the cholera or ETEC vaccine formulated (A) in water (B) in bicarbonate-citric acid buffer (Recip AB, Stockholm) or (C) in a rice syrup based electrolyte buffer, CeraVacx (Cera Products Inc., Columbia, Maryland). One group in both vaccine groups will be given vaccine without any buffer, that is when dissolved in water. The best formulation will be used in further studies described below to study other interventions.

Sample size: Approximately children will be studied in each of three groups ($n=102 \times 3= 306$; $102 \times 3=306$).

Time frame: Within first 6 months of the initiation of the study.

2. Effect of breast feeding on vaccination

Breast fed infants aged between 6 month -2 years will be given the cholera and subsequently the ETEC vaccine. The children will be withheld from breast-feeding for a period of about 3 hours before ingestion of the vaccine and one hour after. In two weeks time a second dose will be given and the same protocol used. Age matched children will be allowed to breast feed within an hour of taking the oral vaccine. Only breast milk will be withheld and children will be allowed to drink

Age matched control children will be given breast milk without limitations.

Sample size- About 228 children will be studied ($57 \times 2=114$ for cholera vaccine; $57 \times 2=114$ for ETEC vaccine).

Principal Investigator: Last, first, middle [name]

Time frame: Within 6 months -2 years of the initiation of the study.

3. Effect of zinc on the immunogenicity of ETEC and cholera vaccine in young children

We would like to study the effect of zinc on the immunogenicity of oral cholera and ETEC vaccine.

Our recent studies have shown zinc enhances the antibacterial antibody responses in toddlers (2-5 years of age) given the oral killed cholera or the ETEC vaccine. We hope that it will also have an effect of improving the immunogenicity in younger children 6-24 months of age who are given the cholera or ETEC vaccine. For this purpose we will supplement children 6 months -2 years of age with daily zinc sulfate (10 mg/day) for two weeks prior to immunization and for the duration of the study. Two doses of the oral killed vaccine will be given two weeks apart and studies continued until a week after the second dose. Thus the study will be undertaken for a period of about 5 weeks in total. A comparison group will be given the vaccine two weeks apart without any zinc supplementation.

Sample size- A total number of 300 children will be studied (75x2= 150 for ETEC vaccine related; 75x2= 150 for cholera related groups for 2 vaccines, with and without zinc).

Time frame: Within 6 month -2 years of the initiation of the study.

Overall design for the vaccine studies:

The vaccine studies will be carried out at the Mirpur field site in urban Dhaka. For both the cholera and ETEC vaccines, two doses will be given 14 days apart. The reactogenicity will be monitored for 3 days after intake of each dose of the vaccine. In the case of the children 6 months to 2 years of age, active surveillance will be carried out by the field staff in the homes by visits every day for 3 days after intake of the vaccine. Since the ETEC and cholera vaccines have generally been found to be safe at the doses being used, passive surveillance has been used in most studies in the case of both adults and children carried out so far. We are however using more precaution by carrying out active surveillance for the children.

Blood and stool samples will be collected prior to immunization and 7 days after intake of each dose of the vaccines in volumes indicated for the immunological assays (Appendix-1-7). They will not be allowed to eat or drink one hour before and after intake of the vaccine except where specified where the duration will be longer. Only when the effect of breast feeding on the immunogenicity of the cholera and ETEC vaccine will be studied the children will be withheld from breast feeding for 3 hours prior to and one hour afterwards. They can drink water during this period.

Sequential progress of the vaccine studies: The vaccine studies will be carried out in a planned and organized manner as has been shown in Appendix 2. Some of the studies will be run in parallel. We hope that by doing this we will be able to maintain a smooth flow and momentum in the study and keep the committees aware of the progress and if necessary make changes as and when thought necessary. In addition this will help us analyze the data and make it available for dissemination, which will be helpful in progressing to Phase III studies of the different components.

Selection of study subjects for vaccine studies:

Healthy children (6 months to 2 years of age) both males and females who have not enrolled in any other research study including that are being conducted by ICDDR,B will be recruited from the urban slums of Mirpur.

Before entering into the study, subjects in the different age groups will be screened from the slums and history recorded and their consent to participate in the study will be obtained (Appendix 4a-4c). We have

previously observed that at least 60% of the families agree to participate in the study. The volunteers prior to enrollment in the study will be carefully examined by a physician. A detailed history of the volunteer of previous immunizations, nutritional status, recent illness (as outlined below) that can compromise the immune system, family background etc. will be taken (Appendix-4a-c). The volunteers should be free from any chronic disease or any recent illness that may compromise the immune system. Children will be excluded from enrollment if interviewers find: (a) a history of chronic gastrointestinal disorder, (b) diarrhoeal illness in the past 2 weeks (diarrhoea being defined as passing of ≥ 3 loose or liquid stools in 24 hours) (c) febrile illness in the preceding week, or (d) other serious chronic illness (e) had antibiotic treatment at least 7 days prior to the enrollment in the study (f) children suffering from third degree of protein energy malnutrition (PEM). The nutritional status of the children to be recruited for the vaccine studies will be monitored using anthropometrical measurements (weight-for-age, and weight-for-length/height). Children below -2SD for weight for height/length of the NCHS median will not be enrolled. Children who have received zinc in the past two months will also not be recruited.

We plan to recruit children in the 6 month -2 year range for immunization.

Baseline evaluation of samples:

Stool examination: A routine stool microscopic examination and culture for *V. cholerae* O1/O139 and ETEC will be carried out four days prior to vaccination. Children whose stools are positive for these pathogens will not be vaccinated since this will interfere in the evaluation of the response to the vaccine. When immunization for the second dose of the vaccine will be carried out (14 days after the first dose) children who have fever or diarrhoea will be excluded from the study.

Zinc: Serum zinc concentrations will be determined at baseline only. Venous blood collected in trace element free vacutainers will be placed in ice until arrival at the ICDDR,B laboratory on the same day. Serum will be assayed by flame atomic absorption spectrophotometry and zinc deficiency will be defined as a serum zinc concentration <60 ug/dl (31).

Vaccine, administration and allocation: Both the cholera and ETEC vaccine are produced by the Swedish Bacteriological Laboratories (SBL Vaccin AB Stockholm, Sweden). One dose of the ETEC vaccine contains 1.0 mg BS plus 2×10^{10} formalin inactivated bacteria each of 5 strains of ETEC expressing 6 colonization factors. The oral inactivated cholera vaccine (Dukoral) consists of killed bacteria prepared from individual batches of O1 El Tor and classical *V. cholerae* to include both LPS and protein antigens and also contains recombinant BS. One dose of vaccine contains 1.25×10^{11} CFU of the killed whole cell vaccine plus 1 mg of BS developed in Sweden and also produced by SBL. New batches of ETEC vaccine containing 1.0 mg of BS plus about 10^{11} formalin inactivated bacteria expressing colonization factors will be prepared for the study. For all children a quarter dose of the CF-BS-ETEC vaccine will be tested since some adverse events of vomiting was observed with the higher dose (Qadri et al. in manuscript).

Informed written consent will be taken from the parent/guardian for the children for the immunization and for the permission to draw blood and obtain stool samples (Appendices).

Immediately before use individual doses of the liquid form of the vaccine will be mixed with the reconstituted bicarbonate or CeraVax buffer. For children, the vaccine (either the individual ETEC or cholera vaccine) will be dissolved in 20 ml (total 4 teaspoon) of a raspberry flavored bicarbonate buffer-citric acid buffer [the buffer is prepared by adding 100 ml water to a sachet of bicarbonate buffer (2 g bicarbonate; 750 mg of citric acid; Recipe AB, Stockholm) which will be used to prepare the vaccine dose. The vaccines will be mixed with syrup of the CeraVax buffer (from one buffer sachet; each sachet of CeraVax buffer contains 2 g of sodium bicarbonate, 0.5 g of trisodium citrate and 7 g of rice syrup solids in 150 ml volume). For the children, 20 ml of either buffer will be used for the formulation. This is the procedure followed for immunization of children in the youngest age groups in our recent studies (Qadri et al. ongoing studies) and has been found suitable since in most cases the total dose of the vaccine was ingested. In case of the studies on the effect of different buffers and amounts on immunization. A third group will be given the vaccines in 20 ml of water.

For studies of zinc on the immunogenicity of the ETEC and/or cholera vaccine, children 6 months-2 years of age

Principal Investigator: Last, first, middle [name]

will be tested. The children will be given zinc or no supplement 10 days prior to immunization. All children will receive vitamin A supplement as is necessary for the different age groups (e.g. 200,000 IU for 1-2 year old children every 6 months as is the procedure in Bangladesh). The intake of the micronutrients will be initiated 10 days before the first dose and will continue up to 7 days after the second dose of the vaccine (that is for a total of 32 days as shown in appendix 7).

Both the cholera and ETEC vaccine have been extensively tested in Bangladesh and other countries of the world. We will however obtain permission from the Bangladesh Drug Administration before importing and using the vaccine described in this project.

Sample collection and laboratory analysis:

Coding of samples

Although the study is an open design, the clinician in the field will code the samples before sending them to the laboratory so that the laboratory personnel will be blinded when the analyses are carried out. The laboratory will only know if the samples have to be analyzed for the cholera or the ETEC vaccine immunological responses.

Samples from vaccines that will be collected at 3 time points will be tested for antibody responses. From blood PBMC will be separated for preparation of antibody in lymphocyte supernatants (ALS, Qadri et al. 2003). ALS and serum samples collected from vaccines at the preimmune (day 0) and post-vaccination days (day 7 and day 21) will be tested for antibody responses. ALS and sera from vaccinees receiving the CF-BS-ETEC vaccine or the cholera vaccine will be tested for the IgA antibody responses to different antigens including (for ETEC CFA/I, CS1,CS2,CS3,CS4,CS5, for cholera vaccine to LPS and to CTB for both). Using fecal extracts from the vaccinees at the 3 time-points, IgA antibody responses to CFA/I, V. cholerae O1 LPS and CTB will be measured. These procedures are already set-up in the laboratory of the investigators (Qadri et al. 2000,2003). Further to test the immunogenicity of the cholera vaccine we will test the vibriocidal antibody response at the 3 time points mentioned above as well as the response to LPS (O1 Ogawa and Inaba) using sera. In addition, the IgA and IgG antibody responses to rCTB will be measured in those being immunized with the cholera or the ETEC vaccine. The serum zinc level will also be assessed at the baseline in all the children since it may have an effect on the response to the intervention(s) and the vaccination.

Safety Monitoring Committee

[name] (CSD) will serve as the Chairperson of the committee. Other members include [name].(CSD), [name] (CSD) and [name] (LSD). The members are in no way involved with the project.

Safety endpoint and safety evaluation

The primary end point for evaluating safety will be defined as the occurrence of any of the following diarrhoea, vomiting or abdominal cramps of at least moderate grade. Diarrhea will be defined as three or more loose or liquid stools in any 24-h period. A measured oral or rectal temperature above 38°C will be considered a fever.

Overall laboratory tests for the project

Vaccinees:

Stools will be cultured on MacConkey agar and tested for colonization factors of ETEC by dot blot immunoassay

Principal Investigator: Last, first, middle [name]

techniques and for the enterotoxins LT and ST (Svennerholm and Wiklund, 1983; Svennerholm *et al.*, 1986, Qadri *et al.* 2000). Stools will also be plated on TTGA (taurocholate-tellurite-gelatin agar) and gelatin agar overnight (Gelatin agar) (Difco, Detroit, MI). Suspected *V. cholerae* O1 and O139 colonies will be identified by slide agglutination using monoclonal antibodies (Qadri *et al.* 1995).

Plasma separated from blood will be used to test for the antibody response to the cholera and ETEC vaccine specific antigens in the volunteers as necessary. To test the response to the cholera vaccine, vibriocidal antibodies and cholera toxin specific antibodies in the IgA and IgG isotypes will be measured (Jertborn *et al.* 1986). For the response to the BS-CF-ETEC vaccine, response to the different CF antigens in the IgA isotype and to CTB in the IgA and IgG isotype will be measured (Qadri *et al.* 2000). Antibody in lymphocyte supernatants will be collected from cultured PBMC (Qadri *et al.* 2003).

Field site for studies planned in the project:

Children from the urban slums in the Mirpur, Dhaka city area will be recruited in the study. We have been conducting other studies at this site (Protocols 99033, 98009,2000-027, 2000-017). A field station has been set up for the past 8 years for carrying out ETEC and cholera vaccine studies. Mirpur is about 6 km northwest of ICDDR,B. The area has been used for field studies since 1987. It is about 10 sq km in radius and divided into 14 sections. We have previously carried out studies in sections 10, 11 and 12. Each section is again divided into camps. A population of about 300,000 is estimated in these three sections. It is believed that there will be an adequate number of adults as well as infants and children in the different age groups to meet the requirement for the study. We plan to carry out the vaccinations at this field site. Subjects will only be recruited into the study if they have not been enrolled in any other protocol being carried out by ICDDR,B or other institutions which require vaccine or nutritional interventions for the duration of this study.

Facilities Available

Existing field, hospital, laboratory and office facilities are adequate and are outlined. The purified antigens used for the study will be supplied by the collaborating laboratory at Goteborg University Sweden.

Recruitment of volunteers and field site for study:

The volunteers will be recruited from the urban slums in Mirpur in Dhaka for the study. The project office will be around the same area which is at present being used for other studies ongoing in ICDDR,B (projects: 98009, 99033, 2001-027,2000-027).

Clinical and field facilities:

The clinicians in the study will coordinate the clinical component of the study in the ICDDR,B hospital and in the Mirpur field site. Clinical facility needed in the study will be provided by the study physicians and other clinicians at the Clinical Research and Service Centre of the ICDDR,B hospital in Dhaka.

Laboratory facilities:

Existing laboratory facilities are adequate.

Data Analysis:

Methods to ensure data quality

All samples will be coded before reaching the laboratory and blinded until immunological analyses have been completed.

Data management; To maintain consistency the data forms will be reviewed by the investigators. This will be carried out to ensure the completeness and accuracy of the data. After editing, data will be entered in an appropriate data entry program that will be suitable for the study.

The data will be entered into a computer and a data base created. Data will be analyzed using an appropriate statistical programme, EpiInfo version 2000 or SPSS. Descriptive statistics will be generated using EpiInfo and SPSS for Windows (Version 10.00) or SigmaStat.

Statistical analysis will be carried out using appropriate parametric and non parametric tests. Overall rates of adverse reaction and seroconversion will be compared by χ^2 test with Yates correction or by the Fisher exact test. Seroconversion for the vibriocidal response will be defined as ≥ 4 fold rise in reciprocal serum vibriocidal titer from pre to post vaccination. If necessary, vibriocidal antibody titers will be transformed to logarithms to better approximate normality.

For the CF, LPS and CTB specific responses in ALS and serum samples, a ≥ 2 fold response from baseline to post vaccination will be considered a positive response. The increase in responses due to any intervention should be at least 2 fold or higher increase from that seen in the vaccinees in whom any intervention has not been carried out. We will therefore expect to see a 4 fold higher increase in the intervention group. Differences in the geometric mean titers (GMTs) of the antibody will be compared by the Mann-Whitney test or the Wilcoxon Rank Sum Test or the Student's t-test as found appropriate.

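### The cholera breast-feeding comparison takes its 57 per group from the ETEC responder rate, giving about 55% power for the stated 50% improvement

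*Protocol*

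**What the plan says.** The sample-size paragraph under Research Design and Methods opens with one rule for all components: "The sample size has been calculated in the different interventions", "using a one sided hypothesis and confidence of approximately 95" per cent, "a minimum detectable difference in mean (MDD) of 50% improvement over baseline", and "with 15% for dropout adjustment". No power is stated.

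Three group sizes follow:

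- **Formulation.** From a 36% vibriocidal responder rate to the cholera vaccine at ages 2-5 years, "the sample size of each group in the two buffer components and in the formulation in water will be 102".
- **Breast feeding.** From a 55% CF-specific responder rate to the ETEC vaccine at 6 months to 2 years, "the sample size of the each group of the breast feeding component will be 57".
- **Zinc.** From cholera-vaccine results of 36% without and 66% with zinc, "the sample size of each group on the zinc supplementation component will be 75".

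Section 2, Effect of breast feeding on vaccination, applies the breast-feeding figure to both vaccines: "Sample size- About 228 children will be studied", as 57 x 2 = 114 for cholera and 57 x 2 = 114 for ETEC. Appendix 2 repeats these counts. Data Analysis plans to compare seroconversion by chi-square with Yates correction or by Fisher's exact test.

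**The concern.** The breast-feeding size is calculated from one vaccine's responder rate, on one antigen, and used for a different vaccine with a lower stated rate. For a fixed relative improvement, a lower baseline means a smaller absolute difference (18 points from 36%, 27.5 points from 55%) and so needs more children. The protocol's own cholera calculation gives 102, yet the cholera breast-feeding comparison has 57. That mismatch can be seen without assuming any power.

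Temporary withholding of breast milk is one of the three stated hypotheses. If the comparison is reported as sized for a 50% improvement when it is not, a non-significant cholera result is easily misread as evidence that withholding makes no difference. The opening sentence also fails to describe the zinc component.

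**Working it through.** **Inputs from the protocol.** One-sided alpha 0.05 (z = 1.645); 15% dropout; cholera baseline 36%; ETEC baseline 55%; equal groups. The 50% improvement is read as relative: 36% x 1.5 = 54% and 55% x 1.5 = 82.5%. An absolute 50 points added to 55% would exceed 100%.

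**Assumptions.** Power is not stated, so it is solved for. Evaluable numbers are 57 x 0.85 = 48.45 (48), 102 x 0.85 = 86.7 (87) and 75 x 0.85 = 63.75 (64).

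**Formula** (pooled two-proportion normal approximation, n evaluable per group, pbar = (p1+p2)/2):

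power = Phi{ [ |p2-p1| sqrt(n) - 1.645 sqrt(2 pbar(1-pbar)) ] / sqrt(p1(1-p1) + p2(1-p2)) }

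**Step 1: the plan's own sizes, each on its own basis.**

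- 102, 36% vs 54%: (1.679 - 1.157)/0.692 = 0.754, power about 77%.
- 57, 55% vs 82.5%: (1.905 - 1.078)/0.626 = 1.321, power about 91%.
- 75, 36% vs 66%: (2.400 - 1.163)/0.674 = 1.834, power about 97%.

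One power does not give all three. Solving the same formula for n, rounding up and dividing by 0.85, 36% vs 54% needs 111, 129 or 152 per group at 80%, 85% or 90% power, while 55% vs 82.5% needs 42, 48 or 56. So 57 fits about 90% power and 102 fits about 77%. Continuity correction, unpooled variance, arcsine, two-sided testing and other dropout inflation were also tried, and none gave both 57 and 102 at one power.

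**Step 2: cholera breast feeding, 36% vs 54%.**

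At n = 48: (1.247 - 1.157)/0.692 = 0.130, power 55%.

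For the planned test, reject when (difference - 1/n)/sqrt(2 pbar(1-pbar)/n) >= 1.645, with pbar now the observed pooled proportion, and sum the binomial probabilities of all such outcomes:

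| Evaluable per group | Uncorrected | Yates (exact sum) |
|---|---|---|
| 48 | 55% | 47% |
| 57 (no dropout) | 62% | 56% |

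**Step 3: sensitivity to the baseline** (48 evaluable, 50% relative improvement, uncorrected):

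| Baseline | Improved | Power |
|---|---|---|
| 30% | 45% | 45% |
| 36% | 54% | 55% |
| 40% | 60% | 63% |
| 45% | 67.5% | 72% |
| 55% | 82.5% | 91% |

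**Step 4: what 57 per group can detect from 36% with 80% power** (48 evaluable). Uncorrected: 61%, a relative improvement of 61/36 - 1 = 69%. With Yates: 64%, since 36% vs 64% has 81% power and 36% vs 63% has 78%; this is 64/36 - 1 = 78%.

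**Step 5: zinc.** 66/36 - 1 = 83%, not 50%.

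**The case against.** The strongest reply is that 36% may be the wrong baseline here. It comes from children aged 2-5 years given the vaccine in standard buffer, while this component enrols children of 6 months to 2 years who receive whichever formulation is chosen. If the cholera rate were near 55%, 57 per group would suffice. That stands as a caveat on the 55% figure, and it cuts both ways, since a lower rate gives less power. It does not rescue the plan: 36% is the only cholera rate given, and the protocol uses it to size the cholera formulation arms in the same age group. The power figure also covers vibriocidal responder status only. Titre comparisons and other cholera readouts are planned, so a null result would not be wholly uninformative.

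A reader might go further in three ways that the protocol does not support.

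- **That zinc is underpowered for cholera.** It is openly sized on a cited 36% to 66% effect with the cholera vaccine, and has about 97% power for it. Only the blanket 50% sentence is wrong for zinc.
- **That the ETEC formulation arms are far too large.** Against 55% to 82.5% they have about 99% power, but the component also asks whether buffer can be omitted with immunogenicity retained, and gives no margin. With an assumed 20-point non-inferiority margin at 55%, n = (1.645 + 0.842)^2 x 2 x 0.55 x 0.45 / 0.20^2 = 77, or 91 per arm with dropout at 80% power, and 125 at 90%. With 15 points it is 162 to 223. On that aim 102 is not excessive.
- **That children should move from ETEC to cholera arms.** Cutting the ETEC formulation arms would weaken that aim. Seven cholera arms of 111 would be 777 children against 570 planned, and at 94 evaluable per arm power is about 75% under Yates, not 80%.

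The missing power alone might be left to an analysis plan. The inconsistency among the fixed group sizes cannot be.

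**Conclusion.** The point holds for the cholera breast-feeding comparison. Its 57 per group comes from the ETEC rate, whereas the plan's own cholera calculation for the same 50% improvement is 102. Power for 36% against 54% is about 55%, or 47% under Yates, compared with about 91% uncorrected for ETEC with the same 57. This assumes one-sided testing at 5%, 15% loss from 57, a relative reading of the 50%, and a 36% baseline carried over from older children. The shortfall persists at any baseline near 36% and goes away only if cholera responders are about as common as ETEC responders. Two lesser faults go with it: the 50% sentence does not describe zinc, and the three sizes imply different, unstated powers (about 77%, 91% and 97%).

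**What to change.** Rewrite the sample-size paragraph without changing enrolment:

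1. Give the responder rate for each vaccine, noting that the cholera rate comes from ages 2-5 years, and show how the result changes over a range of baselines.
2. State one alpha, one power and the test assumed.
3. For each component and each vaccine, give the difference that the planned group size can detect under the planned test. For cholera breast feeding at 80% power and 48 evaluable, this is about 36% to 61% uncorrected, or 36% to 64% with Yates.
4. State that the zinc size rests on 36% to 66%, and limit the 50% sentence to the comparisons it describes.

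The cost is a text change only; the counts in Appendix 2 stay as they are. The downside is that the cholera breast-feeding comparison must be presented as able to detect only a larger effect, a relative improvement of about 70% to 80% instead of 50%.

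### The breast-feeding component is age matched, but the rate and rank tests the protocol names make no use of age; an age-stratified analysis would be a small, nearly free improvement

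*Protocol*

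**What the plan says.** The protocol's section 2, Effect of breast feeding on vaccination, enrols breast-fed children aged 6 months to 2 years and twice calls the comparison children age matched: "Age matched children will be allowed to breast feed within an hour of taking the oral vaccine" and "Age matched control children will be given breast milk without limitations". It does not say whether matching is by pair or by group, how close in age the children must be, or how matching is carried out.

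The Sample size paragraph under Research Design and Methods states that "the sample size of the each group of the breast feeding component will be 57", with a one-sided hypothesis, about 95% confidence, a 50% improvement and 15% for dropout. Section 2 and Appendix 2 use the same 57 per group (114 children) for each vaccine.

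Data Analysis names one set of tests for all components. Rates of adverse reaction and seroconversion are compared by chi-square "with Yates correction or by the Fisher exact test". Geometric mean titres "will be compared by the Mann-Whitney test or the Wilcoxon Rank Sum Test or the Student's t-test as found appropriate". No paired, age-stratified or age-adjusted method is named. The section does open with a general promise of suitable parametric and nonparametric methods.

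**The concern.** Matching is usually done because the matching factor is thought to affect the outcome. If it does, responses in the two groups are positively correlated through age. A test that assumes independent groups then overstates the variance of the difference, so its true level falls below nominal and it gives up some power to an analysis that uses age.

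The protocol gives some reason to think age could matter. Its background says that gastric pH is higher in younger children, and reads the fall in ETEC illness with age as developing immunity. Age matching is also the only balancing device that the text shown describes for this component, and the named rate and rank tests cannot restore age balance if losses disturb it.

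At stake is a little efficiency and some robustness, not a false-positive risk.

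**Working it through.** **Inputs from the protocol.** One-sided 5% level; 57 per group; 15% dropout, so 57 × 0.85 = 48 evaluable; 50% improvement read as relative. ETEC responder rate 55%, so 82.5% after improvement. Cholera vibriocidal response 36% (from children aged 2-5 years), so 54%.

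**Inputs assumed.** Power is not stated; 90% is inferred below. The protocol gives neither an age gradient within 6-24 months nor a within-match correlation. Ages are taken as uniform, with a responder rate rising linearly from 6 to 24 months: 20% to 52% or 10% to 62% for cholera (both average 36%), and 40% to 70% for ETEC (average 55%).

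**1. The plan's own figure.** For two independent proportions with pooled variance, p̄ = (0.55 + 0.825)/2 = 0.6875, and

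n = [1.645 × √(2 × 0.6875 × 0.3125) + 1.282 × √(0.55 × 0.45 + 0.825 × 0.175)]² / 0.275² = (1.078 + 0.802)² / 0.0756 ≈ 47.

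Allowing for dropout, 47/0.85 = 55.3, so 56, within 1 of the stated 57. The component fits an independent-groups calculation at 90% power. Other settings also come close (for example one-sided 85% power with continuity correction, also 56).

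**2. Correlation that age matching could induce.** With perfect matching, phi = variance of the age-specific rate / [p(1 − p)], and a linear rise of width w has variance w²/12.

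- Cholera 20-52%: (0.32²/12)/(0.36 × 0.64) = 0.037
- Cholera 10-62%: (0.52²/12)/(0.36 × 0.64) = 0.098
- ETEC 40-70%: (0.30²/12)/(0.55 × 0.45) = 0.030

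**3. True level of an unstratified test.** In large samples this is 1 − Φ(1.645/√(1 − phi)): 0.050 at phi 0, 0.046 at phi 0.05 and 0.041 at phi 0.10. Simulation of the uncorrected test at 48 per group gives about 4.4% to 5.0% on the assumed slopes. The departure is small and always in the conservative direction.

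**4. Power of the recommended analysis.** Simulation with 48 per group, one-sided 5%, no continuity correction, and a Mantel-Haenszel test in three age bands:

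| Setting | Unstratified | Three age bands |
|---|---|---|
| Cholera, 20-52% slope | 56% | 58% |
| Cholera, 10-62% slope | 56% | 61% |
| Cholera, no age slope | 55.9% | 54.6% |
| ETEC, 40-70% slope | 90.9% | 91.5% |

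The cholera rows with a slope apply the 50% improvement proportionally at every age; a constant 18-point difference gives somewhat smaller gains. For ETEC a proportional effect cannot hold throughout (0.70 × 1.5 = 1.05), but the gain stays under 1 point with a constant difference as well.

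**5. Comparison with another choice in the same sentence.** With no correlation at all, Yates and Fisher already run at about 3.1% one-sided at the ETEC rate, and Yates at about 3.5% at the cholera rate. That correction costs more than plausible age matching does.

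**The case against.** The strongest reply is that Data Analysis is a generic paragraph for the whole programme, leaves room for whatever tests suit, and that covariate adjustment for one component normally belongs in a statistical analysis plan. That stands in part: the absence of fuller detail is no fault. What remains is that the protocol states a matched design and names rate and rank tests that ignore the matching factor.

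Three stronger readings are tempting but not supported.

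- A reader might infer that all the tests listed treat the groups as independent. Student's t-test could be paired, and the opening wording does not exclude a paired or stratified method.
- A reader might infer individual pairs, and so a large loss against McNemar's test. The protocol describes no pairs, matched sets or age tolerance, and the sizing fits two independent groups. A large loss would also need a within-pair correlation well above the 0.03 to 0.10 derived from the assumed slopes.
- A reader might infer that the component falls short of its planned power because of the tests. It does not: unstratified power stays level or rises slightly with positive correlation. The low cholera power of about 56% arises because the group size was derived from the ETEC rate; matching neither causes nor cures that.

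The argument from losses is also modest. Children with fever or diarrhoea at dose 2 are excluded (Baseline evaluation of samples). If losses are unrelated to age and arm, the difference in mean age has a standard deviation of about 0.4 month. On the 20-52% slope (32 points over 18 months, 1.8 points per month) that is 0.4 × 1.8 ≈ 0.7 point. Losses that differ by both age and arm could do more, but nothing in the protocol suggests them.

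**Conclusion.** The point holds as a minor one. The design is described as age matched, and the rate and rank tests named do not use age. If response rises with age within 6-24 months, those tests are slightly conservative and give up about 2 to 5 points of power for cholera and under 1 point for ETEC against an age-stratified test. If age does not matter, stratifying loses up to about 1 point. These sizes rest on assumed slopes, uniform ages, 48 evaluable children per group and the 50% relative improvement. Type I error is not inflated, and this point gives no reason to change the 57 per group.

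**What to change.** For the breast-feeding component, say in Data Analysis how the age matching is done, and name tests that use age:

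- **Responder rates:** a Mantel-Haenszel test and risk difference stratified by age band (for example 6-11, 12-17 and 18-24 months), or logistic regression on group and age.
- **Titres:** linear regression of log titre on group and age, or a van Elteren (age-stratified rank-sum) test.

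Use age bands rather than strict pairs: no pairs are described, and exclusions at dose 2 would break them and discard the partner's data. The bands suit either form of matching.

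The cost is a change of wording. Date of birth is already on the screening form (Appendix 5a), and no extra child, visit or sample is needed. The only statistical price is the loss of up to about 1 point of power if response does not vary with age.
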